**This study revealed no significant side effects and the primary pre-specified safety data**

**showed no changes in levels of potassium, glucose, uric acid, creatine kinase or alanine aminotransferase levels (data not shown). The subjects also displayed no changes in hemodynamics, although the hematocrit dropped from  $40 \pm 3$  to  $39 \pm 3$  (percent) and the platelets dropped from  $220 \pm 40$  to  $200 \pm 30$  ( $\times 10^3/\mu\text{L}$ ), both  $\pm\text{SD}$  with a  $p$  value  $< 0.05$ . The modest reduction in hematocrit, hemoglobin and platelet count were suspected to result from the repeated daily laboratory blood draws over the nine-day study.**

At the same time we recently found that NR improves mitochondrial oxidative phosphorylation capacity in parallel with suppressing in-vitro inflammation in human peripheral blood cells. Hence, given the role of skeletal muscle in heart failure inflammation, we will also measure serum cytokine levels in response to NR in this protocol.

Additional studies have been completed or are ongoing using NR to study effects on mitochondrial biology related conditions including aging (at the University of Colorado in Boulder – PI - Drs [name] - actively recruiting) and in heart failure (University of Washington in Seattle – [name] [name] - actively recruiting). Based on their prior pharmacokinetics study described above the University of Seattle team are using 1000mg BID in their Heart Failure protocol. To date, they have recruited 15 subjects and the dose of 1000 mg BID has been well tolerated. We therefore propose to use the same, 1000mg BID dosing.

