## **2. Objectives**

A pilot study will be undertaken where up to 25 participants with clinically stable, systolic heart failure (LVEF  $\leq 45\%$ ) will be enrolled with a goal of having 15 subjects complete the treatment. NR will be increased at two weekly intervals by 250 mg/dose (500 mg/day) to a final dose of 1000mg PO BID (2000 mg/day). Clinic visits with bi-weekly labs during dose escalation will assess HF symptoms and monitor proBNP, CBC, HbA1C, ALT, CK, insulin/glucose, uric acid, electrolytes, BUN/Cr levels. Serum NAD+ levels will be measured at baseline, 12 and 16 weeks and baseline (within 3 months of enrollment) and 12 week echocardiograms will be performed to measure left ventricular systolic and diastolic function.

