### 3. Study Design and Procedures

The study design is an open label pilot study with subjects serving as their own controls. The outline of the clinical protocol is shown in a tabular schematic below.

Visit #	1	2	3	4	5	6	7A/B	8	9
Weeks	-1 to -3	0	0+ 1-2 days	2	4	6	12	12 + 1-2 days	16
Procedures									
History	X	X		X	X	X	X		X
Physical exam	X			X	X	X	X		X
Initiate NR/dispense meds			X						
Dose adjustment				X 	X 	X 			
Stop NR								X	
Urine pregnancy test	X 	X 	X 				X 	X 	X 
Clinical blood tests	(X)	X 	X 	X	X	X	X 	X 	X
NMR spectroscopy		X 	X 				X 	X 	X
CPET		X 	X 				X 	X 	
Echo	X*						X		
Research blood		X 	X 					X 	
Skin biopsy		X 	X 						
AE assessment				X	X	X	X	X	X
Concomitant meds/tx	X			X	X	X	X	X	X
Study drug adherence				X	X	X	X		
Key:									
(X) Performed only if baseline laboratory studies not performed during routine testing within 6 months									
X Procedure performed									
 Increase NR dose by 250mg BID									
 Pregnancy test will only be performed in women with childbearing potential. It can be completed at Visit 1, 2 and/or 3 and Visit 7 or 8									
 Skin biopsy will be completed at either Visit 2 or 3.									
 NMR spectroscopy, clinical and research blood, and CPET testing can be performed at either Visit 2 or 3 for baseline timepoint and Visit 7 or 8 for end of treatment timepoint.									
* Procedure is optional (Echo is optional on Visit 1 if PI feels there is an adequate and timely historical Echo)									
Visits 1, 4, 5, 6, and 7 may take place at either WRNMMC or NIH Clinical Center.									
Visits 2, 3, 7B, 8, and 9 will take place at the NIH Clinical Center									

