### **Visit 3 (Week 0 + 1-2 days, NIH CC)**

#### **The following procedures will be performed at Visit 3:**

- Dispense NR: Level 1 ( 250mg PO BID to initiate supplementation in evening after visit 3).
- Dispense Level 2-4 bottles of NR: Level 2 (500mg PO BID – to initiate after visit 4), Level 3 (750mg PO BID – to initiate after visit 5) and Level 4 (1000mg PO BID – to initiate after visit 6 and maintain through visit 7).

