### **Visit 4 (Week 2, WRNMMC or NIH CC)**

#### **The following procedures will be performed at the follow-up visits (Day 14±3):**

- Medical history, physical examination, current medical treatments
- Blood draws will analyze: CBC+Diff, proBNP, HbA1C, uric acid, ALT, CK, Chemistry panel (electrolytes, glucose, blood urea nitrogen and creatinine) and insulin levels
- Record of adverse events, if any
- Study drug adherence with pill count and collect Level 1 NR 250mg PO BID bottle.
- Record of concomitant medications or interventions, if any
- Communicate the initiation of Level 2 NR 500mg PO BID in evening after visit 4

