## **Visit 5 (Week 4, WRNMMC or NIH CC)**

**The following procedures will be performed at the follow-up visits (Day 28±3):**

- Medical history, physical examination, current medical treatments
- Blood draws will analyze: CBC+Diff, proBNP, HbA1C, uric acid, ALT, CK, Chemistry panel (electrolytes, glucose, blood urea nitrogen and creatinine) and insulin levels.
- Record of adverse events, if any
- Study drug adherence with pill count and collect Level 2 NR 500mg PO BID bottle
- Record of concomitant medications or interventions, if any
- Communicate the initiation of Level 3 NR 750mg PO BID in evening after visit 5

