## **Visit 6 (Week 6, WRNMMC or NIH CC)**

**The following procedures will be performed at the follow-up visits (Day 42±5):**

- Medical history, physical examination, current medical treatments
- Blood draws will analyze: CBC+Diff, BNP, HbA1C, uric acid, ALT, CK, Chemistry panel (electrolytes, glucose, blood urea nitrogen and creatinine) and insulin levels.
- Record of adverse events, if any
- Study drug adherence with pill count and collect Level 3 NR 750mg PO BID bottle
- Record of concomitant medications or interventions, if any
- Communicate the initiation of Level 4 NR 1000mg PO BID in evening after visit 6

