### **Adverse Event Management**

The principal investigators at WRNMMC or NIH, or designees, will be responsible for assessing adverse events. Information on adverse events will be solicited from subjects through questions from study personnel and information volunteered by the subject. Adverse events will be captured from the start of the first pill taken (day 0) until the completion of the washout phase of the study. The AEs will be attributed (unrelated, unlikely, possibly, probably or definitely) to study supplement and/or disease. This study will utilize the CTCAE version 5.0 for toxicity and adverse event reporting. A copy of the CTCAE version 5.0 can be downloaded from the [https://ctep.cancer.gov/protocolDevelopment/electronic\\_applications/ctc.htm](https://ctep.cancer.gov/protocolDevelopment/electronic_applications/ctc.htm). AEs will be recorded, verified, and followed until satisfactory resolution.

In the event of any treatment-related SAEs, enrollment will be suspended until discussed with the IRB and Clinical Director.

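### After a treatment-related SAE the only pre-specified study-level action is to suspend enrollment pending discussion; no dosing action is set for other subjects on NR, and the sentence has no effect once accrual closes

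*Combined protocol and SAP*

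**What the plan says.** The response to a treatment-related SAE is one sentence in Section 10, Adverse Event Management: "In the event of any treatment-related SAEs, enrollment will be suspended until discussed with the IRB and Clinical Director". It names enrollment and a discussion. It does not mention the dosing of subjects already taking NR.

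Dose escalation is described in Section 3. The footnote to the dose-adjustment row of the visit schedule reads "Increase NR dose by 250mg BID". All the supply is handed over at Visit 3 ("Dispense Level 2-4 bottles of NR"), but each step waits for a visit. At Visits 4, 5 and 6 staff take a history, examine the subject, draw blood, record adverse events and count pills. They are then to do the following:

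- Visit 4: "Communicate the initiation of Level 2 NR 500mg PO BID in evening after visit 4"
- Visit 5: "Communicate the initiation of Level 3 NR 750mg PO BID in evening after visit 5"
- Visit 6: "Communicate the initiation of Level 4 NR 1000mg PO BID in evening after visit 6"

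Section 2 describes the monitoring in this period: "Clinic visits with bi-weekly labs during dose escalation will assess HF symptoms". No visit description states a finding, in the subject or elsewhere in the study, that would withhold the next level.

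Other safety text bears on the point:

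- Section 9 takes a subject off study for a heart failure hospitalization or, on a physician's determination, other severe symptoms, and notifies the IRB.
- Section 10 provides for safety monitoring by the principal investigator at each site, for IRB review while accrual or follow-up is open, and for DSMB review every six or twelve months.
- Section 10 also requires reports within 7 days for serious unanticipated problems and for deaths at least possibly related to the study.

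**The concern.** The trigger is harm attributed to NR, but the stated action protects only people who have not yet joined. A new subject would start at 500 mg/day, the lowest dose, and is kept out. A current subject may, on the written schedule, step up to 1000, 1500 or 2000 mg/day while the same event is being discussed. After the last subject has started there is no enrollment to suspend. The discussion is written only as the condition for lifting the suspension, so the sentence then requires nothing.

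Section 11 classes the study as more than minimal risk without prospect of direct benefit, which is a reason to settle the matter in advance. The cited human experience of NR at 1000 mg twice daily is small: 8 volunteers on incremental doses up to that level over 9 days, and an ongoing heart failure study with 15 recruited, of which the Background says "the dose of 1000 mg BID has been well tolerated". The protocol adds single NR doses up to 1000 mg without toxicity, an ongoing study of 1000 mg daily for 6 weeks, and nicotinamide up to 3000 mg/day for up to 3 years. This is reassuring, but it does not say whether other subjects should step up by 500 mg/day while a related SAE is unresolved.

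**Working it through.** **Text check.** The sections on objectives, study visits, dosing, off-study criteria and safety monitoring were read for any study-level dose hold, escalation pause, dose reduction or stopping rule. None was found. The nearest provisions compare as follows:

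| Provision | Whom it reaches | Dosing action for others on NR |
|---|---|---|
| Enrollment suspension (Section 10) | Future subjects | None |
| Off-study criteria (Section 9) | Affected subject | None |
| 7-day reports (Section 10) | IRB, Clinical Director | None |
| DSMB review (Section 10) | Whole study, every 6 or 12 months | None pre-specified |

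Each subject has 12 weeks on NR, less than the shortest DSMB interval.

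**How often an increase falls due.** The plan gives no figure to reproduce. Inputs from Section 3: steps at Days 14, 28 and 42, with 84 days on NR. Day 0 is taken as the start of NR.

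- Days from which a step is due within 7 days: 3 × 7 = 21. Escalation phase: 21/42 = 50%. All time on NR: 21/84 = 25%.
- Within 14 days: 3 × 14 = 42. Escalation phase: 42/42 = 100%. All time on NR: 42/84 = 50%.

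With the visit windows (Visit 4 Days 11-17, Visit 5 Days 25-31, Visit 6 Days 37-47), the days at risk are the sum of min(gap, W) over the three gaps, where W is 7 or 14 days. If NR stops at Visit 8, 1 to 3 days after Visit 7B (Day 84 ± 5), time on NR runs from 79 + 1 = 80 to 89 + 3 = 92 days.

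- Escalation phase, W = 7: 21/47 = 44.7% to 21/37 = 56.8%.
- Escalation phase, W = 14: 36/47 = 76.6% (visits on Days 17, 25, 47: 14 + 8 + 14 = 36) to 100%.
- All time on NR, W = 7: 20/92 = 21.7% (Visit 5 to 6 gap of 6 days: 7 + 7 + 6 = 20) to 21/80 = 26.3%.
- All time on NR, W = 14: 31/92 = 33.7% (Days 11, 31, 37: 11 + 14 + 6 = 31) to 42/80 = 52.5%.

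Seven days is used because it is the reporting limit. The length of the discussion is not stated.

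**After accrual closes.** The accrual period T is not stated; even accrual over 182, 365 or 730 days without dropout is assumed. The share of subject-days on NR after the last start is 84/(2T): 23.1%, 11.5% or 5.8%. Of those days, the part in Days 0-42 is (42²/2)/(84²/2) = 882/3528 = 25%. An escalation hold could therefore act on 5.8%, 2.9% or 1.4% of all subject-days. The other 75% of post-accrual exposure is already at 2000 mg/day.

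**Dose lost to a hold.** Planned total (Section 6 schedule): 14 × 500 + 14 × 1000 + 14 × 1500 + 42 × 2000 = 126,000 mg. With week 12 fixed, a hold of d days at level L loses d × (2000 − L). For d = 7:

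- L = 500: 10,500 mg lost, 91.7% remains.
- L = 1000: 7,000 mg lost, 94.4% remains.
- L = 1500: 3,500 mg lost, 97.2% remains.

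In each case time at 2000 mg/day falls from 42 to 35 days. The 75% criterion allows a loss of 31,500 mg. That is reached by an escalation hold of 31,500/1500 = 21 days at 500 mg/day or 31,500/1000 = 31.5 days at 1000 mg/day. A 16-day full stop at 2000 mg/day passes it (94,000/126,000 = 74.6%). This assumes the criterion is measured against the original schedule.

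**The case against.** The strongest reply is that clinical staff stand between the bottle and the step. Every increase follows a visit with examination, laboratory tests and adverse event recording, and staff communicate it. The people assessing adverse events are the site principal investigators or their designees, and the principal investigators also monitor safety. They, the IRB or the Clinical Director could pause dosing at once without new text. In a pilot of at most 25 subjects, ad hoc judgment may be thought sufficient. This stands as mitigation: early dispensing does not mean that subjects escalate on their own. It is not a written rule, however, and no safety condition is attached to the step.

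A second reply also stands. An escalation hold does nothing in the interim for subjects in weeks 6-12, who have no increase left and are at the highest dose. For them the gain is a required decision about dosing, not immediate protection.

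Third, an event attributed only as possibly related counts as related under Section 10, so one such hospitalization would delay every escalating subject and shorten time at full dose before the week-12 primary endpoint. That is a real cost, although the same event already suspends enrollment.

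A reader might infer that the protocol directs escalation to continue after a related SAE. It does not; it is silent. Nor does it leave the affected subject without recourse (Section 9) or end oversight with accrual: investigator monitoring, IRB review and 7-day reporting continue. And although Section 11 says consecutive dosing at 1000 mg twice daily has not been reported in humans, the Background's account of the ongoing heart failure study means that dose cannot be called untried.

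**Conclusion.** The point holds as a gap in one stated safety rule. At study level, a treatment-related SAE leads to suspended enrollment and a discussion; other subjects' dosing is not addressed, and the sentence has no operative effect once accrual closes. In the escalation phase a scheduled increase falls within 7 days for half of subject-days on the nominal schedule (45-57% across visit windows). Over all time on NR the figure is 25% (about 22-26%). These percentages assume the event falls at a random time relative to a subject's schedule. It would be wrong to read them as a risk of harm: the documents give no basis for the trigger rate, and neither the discussion time nor the accrual period is stated. Because oversight continues and ad hoc action is possible, this is an inexpensive improvement to make, not a fatal defect.

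**What to change.** Amend the sentence in Section 10 to provide that:

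- any treatment-related SAE, during or after accrual, suspends enrollment and further dose escalation in subjects on NR;
- the current dose may continue unless the investigator or reviewers stop it;
- the suspension lasts until the IRB and Clinical Director, with prompt notice to the DSMB, have discussed the event and stated whether current subjects, including those already at 2000 mg/day, hold, continue, stop or resume escalation.

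Keep Visit 7 at Day 84 ± 5 so that the primary endpoint timing does not move. In Section 9, state that doses held under this rule do not count against the 75% criterion. If that criterion is already measured against instructed doses, this only clarifies it for escalation holds.

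The cost is a few sentences in Sections 9 and 10, using existing reviewers, with no new visits or tests. The downside is an occasional delayed step and somewhat less time at full dose before week 12, sometimes for an event that proves unrelated.

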### **Grading and Attribution of Adverse Events**

**Severity.** Definitions found in the Common Terminology Criteria for Adverse Events version 5.0 (CTCAE v5.0) will be used for grading the **severity** (intensity) of AEs:

1 Mild	Asymptomatic or mild symptoms; clinical or diagnostic observations only; intervention not indicated.
2 Moderate	Moderate; minimal, local or noninvasive intervention indicated; limiting age-appropriate instrumental ADL*
3 Severe	Severe or medically significant but not immediately life-threatening; hospitalization or prolongation of hospitalization indicated; disabling; limiting self-care ADL**.
4 Life-threatening	Life-threatening consequences; urgent intervention indicated.
5 Death	Death related to AE

\*Instrumental ADL refer to preparing meals, shopping for groceries or clothes, using the telephone, managing money, etc.

\*\*Self-care ADL refer to bathing, dressing and undressing, feeding self, using the toilet, taking medications, and not bedridden.

### *Attribution of Adverse Events*

Relationship	Attribution	Description
Unrelated to intervention	Unrelated	The AE is clearly NOT related to the intervention
	Unlikely	The AE is doubtfully related to the intervention
Related to intervention	Possibly	The AE may be related to the intervention
	Probably	The AE is likely related to the intervention
	Definitely	The AE is clearly related to the intervention

### **NHLBI-IRB and CD reporting**

#### ***Serious Events***

**Reports to the IRB and CD:** The PI must report Serious UPs, and Serious PDs to the IRB and CD as soon as possible but not more than 7 days after the PI first learns of the event.

#### ***Non-serious Events***

**Reports to the IRB and CD:** The PI must report all UPs that are not Serious to the IRB and CD, and PDs that are not Serious to the IRB, not more than 14 days after the PI first learns of the event.

### **Deaths**

Deaths possibly, probably, or definitely related to study procedures and interventions will be reported to the Clinical Director within 7 days after the PI first learns of the event.

**Reports at the time of continuing IRB review:** At continuing review, the PI will provide to the IRB a summary of:

- All UPs
- All PDs
- All AEs (except for those granted a waiver of reporting)

### ***Waiver of Reporting:***

#### ***The following adverse events will be listed in the consent and not reported to the IRB:***

- Vasovagal symptoms during blood draws (expected frequency 50%).
- Transient bruising at the site of blood draws (expected frequency 50%).

#### ***The following adverse events will not be recorded or reported to the IRB.***

- Grade 1 adverse events
- Grade 2 laboratory abnormalities not associated with clinical signs or symptoms except for grade 2 elevated liver enzymes, which will be recorded and reported.

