### **Adverse Event Reporting**

**Adverse Event (AE):** Any untoward medical occurrence in a human subject, including any abnormal sign (e.g., abnormal physical exam or laboratory finding), symptom, or disease, temporally associated with the subject's participation in the research, whether or not considered related to the subject's participation in the research.

**Serious Adverse Event (SAE):** A serious adverse event that:

- results in death;
- is life-threatening (places the subject at immediate risk of death from the event as it occurred);
- results in in-patient hospitalization or prolongation of existing hospitalization;
- results in a persistent or significant incapacity;
- results in a congenital anomaly/birth defect; or
- based upon appropriate medical judgment, may jeopardize the subject's health and may require medical or surgical intervention to prevent one of the other outcomes listed in this definition.

**Unanticipated Problem:** An UP is any incident, experience, or outcome that meets all of the following criteria:

1. **unexpected** in terms of nature, severity, or frequency in relation to
  - a. the research risks that are described in the IRB-approved research protocol and informed consent document; Investigator's Brochure or other study documents; and
  - b. the characteristics of the subject population being studied; and
2. **related or possibly related** to participation in the research; and
3. places subjects or others at a **greater risk of harm** (including physical, psychological, economic, or social harm) than was previously known or recognized.

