## **Risks and Discomforts**

- ***Phlebotomy:*** Standard precautions for obtaining human blood samples will be taken. Transient discomfort and minor bruising may occur at the phlebotomy site. Vasovagal symptoms can occur during blood drawing. Blood samples will be obtained by venipuncture. Blood samples will be obtained by a nurse, physician, or other skilled individual. The quantities of blood to be drawn for research purposes will be less than 300 mL, which is consistent with the CC policy as provided in Medical Administrative Series (MAS) 95-9 (revised 05/29/2012): for adults, no more than 10.5 mL/kg or 550 mL (whichever is smaller) will be drawn for research purposes over any 8-week period.
- ***Urine collection:*** There is no risk associated with this procedure.
- ***Nicotinamide Riboside:*** NR is a dietary supplement that is currently available for commercial use with no safety concerns noted to date. A recent PK study of 8 healthy volunteers at University of Washington gave incremental doses up to 1 gram bid over 9 days. The study showed no significant side effects or change in safety data. Consecutive doses of 1000mg BID of NR has not been reported in humans although there is currently an ongoing study at the University of Colorado using 1000 mg daily for 6 weeks. Based on the structural similarities between NR and nicotinamide, and that nicotinamide is a downstream metabolite of NR digestion, it is assumed that any unexpected adverse effects of NR may be similar to those associated with nicotinamide intake. The safety profile of nicotinamide has been well established in multiple species and provides reasonable certainty that the administration of doses of NR up to 1000 mg will not result in an adverse health effect. No significant adverse effects have been reported in clinical trials which have used doses up to the equivalent of 3000 mg/day for up to 3 years to evaluate the

possible benefits of nicotinamide administration to patients with or at risk of developing Type 1 diabetes. In addition, doses of 25 and 42 mg/kg bw/day had no effect on a variety of biochemical parameters, such as those that assessed liver and kidney function.

- **Echocardiography:** There are no known risks to the ultrasound exam.

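### The adverse event waiver keeps mild events out of the record, not only out of IRB reports, and Section 8 plans no summary of adverse events or blood counts

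*Combined protocol and SAP*

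**What the plan says.** Waiver of Reporting (Section 10) contains two lists. The first names vasovagal symptoms and bruising at blood draws, and exempts them from IRB reporting only. The second is headed "The following adverse events will not be recorded or reported to the IRB" and has two entries: "Grade 1 adverse events" and "Grade 2 laboratory abnormalities not associated with clinical signs or symptoms except for grade 2 elevated liver enzymes, which will be recorded and reported".

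The general rule, under Adverse Event Management, is that "AEs will be recorded, verified, and followed until satisfactory resolution". It has no grade threshold, and capture runs from the first pill to the end of washout. Adverse Event Reporting counts abnormal laboratory findings as adverse events.

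On blood counts, Preliminary Results (Section 1) describes a pharmacokinetic study of eight subjects over nine days. Hematocrit fell from 40 ± 3 to 39 ± 3 percent and platelets from 220 ± 40 to 200 ± 30 (×10³/µL), both with p < 0.05. The protocol's explanation is that "The modest reduction in hematocrit, hemoglobin and platelet count were suspected to result from the repeated daily laboratory blood draws". In the present trial a CBC with differential is part of the panel at Visits 4, 5, 6, 7 and 9. Section 8 lists the primary spectroscopy outcome, exercise testing, metabolomics, cytokines and fibroblast work. It lists no summary of adverse events or safety laboratory values.

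**The concern.** Waiving IRB reports of trivial events saves administrative work and loses no data. Waiving their recording loses the data. Adverse events are assessed at Visits 4 to 9, across four dose levels, so study staff would ask about mild symptoms and then leave the answers out of the adverse event log. An event that began at grade 1 and later worsened would have no logged onset, which makes it harder to relate to a dose step. Reviewers could not tell an empty grade 1 row that reflects good tolerability from one produced by the rule.

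This matters because Risks and Discomforts (Section 11) says of the target dose that "Consecutive doses of 1000mg BID of NR has not been reported in humans", and Risk/Benefit Assessment places the study above minimal risk with no prospect of direct benefit.

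The laboratory gap is different. The counts will exist, but nothing in Section 8 commits the study to summarise them.

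**Working it through.** The protocol gives no figure to reproduce. The first two steps compare text; the rest is supporting arithmetic.

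**1. Does the waiver cover recording?** Yes. The first list waives reporting alone, while the second names recording as well. The liver-enzyme exception in "Grade 2 laboratory abnormalities not associated with clinical signs or symptoms except for grade 2 elevated liver enzymes, which will be recorded and reported" treats recording and reporting as two separate acts, so the heading cannot be read as loose wording for IRB reporting only.

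**2. Can both rules be applied to a grade 1 event?** No. Adverse Event Management would have it recorded, verified and followed. The waiver would have it left off the record. Neither passage refers to the other.

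**3. How likely is it that a mild effect occurs and goes unlogged?** Inputs: 15 completers (Section 2) and a true rate p, which the documents do not give and is assumed here. The chance of at least one case is 1 − (1 − p)^15:
- p = 5%: 1 − 0.95^15 = 0.54
- p = 10%: 1 − 0.90^15 = 0.79
- p = 20%: 1 − 0.80^15 = 0.96

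Cases that never exceed grade 1 would be missing from the record at every rate.

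**4. Would the waiver hide falls like those in the pharmacokinetic study?** Relative falls: hematocrit 1/40 = 2.5%; platelets 20/220 = 9.1%. These are shifts in group means, not graded events. Take platelets as normal with the stated means and SDs, and assume a lower limit, since none is given. The share of subjects below it, before and after, is:
- limit 150: Φ(−70/40) = 4.0% and Φ(−50/30) = 4.8%
- limit 140: Φ(−80/40) = 2.3% and Φ(−60/30) = 2.3%
- limit 120: Φ(−100/40) = 0.6% and Φ(−80/30) = 0.4%

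Adverse event counts would hardly move even if every grade were recorded. A shift like this shows in the serial counts or not at all.

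**5. Could the counts already planned describe such a shift?** The SD of the paired differences is not given. With n = 8 and a paired t-test assumed, p < 0.05 requires it to be below 20 × √8 / 2.365 = 23.9 for platelets and 1 × √8 / 2.365 = 1.20 for hematocrit. With 15 completers, the 95% half-width for mean platelet change is 2.145 × SD / √15. That is 5.5 for an assumed SD of 10 and 13.3 for an SD of 24, against a shift of 20. For hematocrit with an SD of 1.20 it is 2.145 × 1.20 / √15 = 0.66, against a shift of 1. A simple table would be informative if variability is in that range.

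**The case against.** The best defence is that this is a general rule with a specific exception, a normal way to draft, and that a cross-reference would settle it. That is a fair reading of how the two passages came about. It does not rescue the outcome: if the exception governs, mild events are unrecorded by design. It is also fair that the aims are mechanistic, that no tolerability endpoint or safety table is specified, and that history is taken at most visits, so some mild symptoms may survive in clinic notes. This limits the stakes.

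Four stronger readings are tempting, and the documents do not support them:
- **The waiver would erase the platelet and hematocrit signal.** It governs adverse event logging. CBC values are collected whatever their grade, and step 4 shows that event counts would not carry the signal anyway.
- **The pharmacokinetic study is the only human experience at this dose.** Section 1 describes an ongoing placebo-controlled heart failure study that assesses tolerability at 1000 mg BID, with 15 subjects recruited and the dose said to be well tolerated. The statement in Risks and Discomforts has to be read beside that.
- **This trial could test the blood-draw explanation.** It is open label with subjects as their own controls. A fall could reflect NR, study phlebotomy, heart failure or other treatment, so serial counts can describe it but not establish its cause.
- **The record is bound to show no tolerability problem.** Symptomatic grade 2 events, grade 2 liver enzyme elevations and everything at grade 3 or above are still recorded.

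**Conclusion.** The point holds in two separate parts. First, the waiver removes grade 1 events and most symptom-free grade 2 laboratory abnormalities from the record and conflicts with the general recording rule. Mild intolerance would therefore be largely absent from the adverse event data by construction. This rests on the text alone; the 54% to 96% range is only an illustration under assumed rates. Second, blood counts are collected but no summary is planned, so changes of the size seen in the pharmacokinetic study may go unreported. The precision figures assume 15 completers and a platelet difference SD between 10 and 24. Neither part touches the primary outcome. This is a modest weakness in the safety record of a small pilot, worth correcting because correction is cheap.

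**What to change.** 1. Reconcile Adverse Event Management with Waiver of Reporting by making the second list recorded but not reported to the IRB, with all grades entered on the case report form. The IRB waiver itself stays.
2. Add to Section 8 a descriptive table of adverse events by grade, and one of change from baseline in platelets, hematocrit and hemoglobin at weeks 2, 4, 6, 12 and 16, from the CBCs already drawn. State that without a control group these tables describe change and do not attribute cause.
3. Say which CBC counts as baseline. The Visit 2 list waives the draw if there is normal blood work within two weeks, and the joint Visit 2 or 3 list says three weeks.

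The cost is extra form entries for at most 25 subjects and a few descriptive tables. No blood draws or IRB reports are added.
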